Official Title: Evaluation of the Wits Workout Wellness Program for Older Adults Document: Study Protocol and Statistical Analysis Plan NCT Number: NCT04928885 Document Date: March 17, 2021

Research Design Wits Workout Program Evaluation

Background and Rationale

About 11% of the U.S. older adult population is at risk for or has subjective cognitive decline¹. While some factors that affect brain health cannot be changed, research has shown that certain lifestyle changes such as participating in regular physical activity, staying socially engaged, and maintaining good heart health make a positive difference that can delay or reduce cognitive decline^{1,2,3}. However, few cognitive brain health programs exist, and those that do are targeted to a specific audience (i.e., Alzheimer's and related dementias). Additionally, these existing programs primarily focus on one health domain (i.e. physical activity, diet)^{4.5} without the additional focus on multi-health domains, which also includes elements such as intellectual engagement, social isolation, stress, sleep, and self-efficacy. **Thus, there is a need for a more holistic cognitive health program aimed toward the general older adult population and particularly those that are underserved (i.e., low income, racialized, rural)**.

Drawing on existing research conducted at the University of Illinois (UI) and other academic institutions, UI Extension Family Life Educators developed *Wits Workout*, a multi-modal workshop series designed to enhance brain health among people ages 50 and older. Wits Workout addresses multiple factors that affect cognitive health such as physical activity, stress, sleep, social isolation. The holistic workshop series is designed to be lay-leader led, interactive, and experiential. Preliminary evaluations demonstrate that this educational series serves a need in reducing isolation, increasing physical activity, promoting intellectual engagement, and enhancing overall brain health in older participants, all of which complement current aging brain health research.

Overall Aims

The aims of the study are to (1) Determine the feasibility and acceptability of Wits Workout among 120 intervention group recipients who receive the program at 8 locations in Illinois; and (2) Use a randomized trial to examine the preliminary efficacy of Wits Workout on changes in the primary outcomes of cognitive functioning, and secondary outcomes of self-efficacy, socialization, sleep, stress and physical activity levels following the 12-week intervention (3 months) and explore maintenance effects at 6 months (3-months post-intervention) compared to a waitlist control.

Hypotheses: At three and six-month posttests, intervention participants compared to controls will differentially improve with respect to (1) PROMIS^{6,7} self-reported cognitive function measures; (2) scores on the Telephone Interview for Cognitive Screening (TICS); and (3) self-efficacy, socialization, sleep, stress and physical activity levels.

Research Design

We propose to conduct a two-arm randomized controlled trial with a treatment (workshop) group and wait-list control group. We will assess participant outcomes at baseline, immediately post-workshop (3-months) and at 6-months to assess maintenance of treatment effects.

Intervention. Wits Workout will take place over 12 weeks, one hour per week. The training will be delivered by 5 UI Extension faculty educators who were trained by the Extension faculty educators who developed the program. Each week includes a themed module with four activities and a training component featuring educational topics such as a) exercising regularly; c) engaging the brain with new and intellectually stimulating challenges; d) participating in social activities; e) getting enough sleep; and f) reducing stress. The workshop will be offered in-person in 8 areas with a target of 20 attendees per urban workshop and 12 attendees per rural workshop for a total of 120 workshop participants. The waitlist control participants (n=120) will be offered the workshop after the 6-month study period is completed. All COVID safety requirements will be in place at the workshop sites. A fidelity assessment tool will be developed by the research team and implemented at all program sites. All Wits Workout leaders will be observed teaching two sessions of the program by one of the study investigators. After the first observation occurs, the fidelity evaluator will debrief with the leader and the evaluator will follow up with a written evaluation that includes strengths, areas of improvement (including ways in which they adhered and/or strayed from the program content and facilitation techniques outlined in the Wits Workout Leader's Guide), and suggestions for increasing fidelity in their teaching. A second observation will occur within the several weeks of the first observation with the goal of continuous process improvement from the first

to the second evaluation. UI faculty educators leading the workshops will record attendance over the 12 weeks and report to the investigative team. Attrition as well as completion rates will be documented based on workshop attendance.

Sample. We will offer Wits Workout to a minimum of 240 older adults (120 treatment and 120 delayed treatment controls) in three urban and five rural areas of Illinois (see

Location	Urban/Rural	Numbers	Waitlist
Chicago Area	Urban	20	20
Chicago Area	Urban	20	20
Champaign	Urban	20	20
St. Joe/Paxton	Rural	12	12
Sterling	Rural	12	12
Mattoon	Rural	12	12
Macomb	Rural	12	12
Marion	Rural	12	12
Total Participants		120	120

Table 1).

Qualitative Outcomes. We will conduct focus groups with participants 3 months after the conclusion of the workshops to learn more about the impact of the workshop on participant's health behaviors and their thoughts about how the program was delivered and evaluated.

[figure not shown]
Outcome Measures. We will examine the effects of participation in Wits Workout on the primary outcome of cognitive functioning and secondary outcomes of improved social satisfaction, self-efficacy, quality of life and sleep, reduced stress, and increased physical activity using the following measurements: Cognitive functioning will be assessed using the PROMIS Cognitive Function- Short Form 8a^{6,7} and the Telephone Interview for Cognitive Status (TICS). ^{8,9} TICS is a brief, standardized test of cognitive functioning designed to be measured over the telephone. Social-satisfaction will be assessed using the Cutrona Social Provisions Scale¹⁰. Self-efficacy will be assessed using the PROMIS Item Bank v1.0 - General Self-Efficacy. ⁶ Sleep will be assessed using the Pittsburg Sleep Quality Index (PSQI).¹³ Stress will be assessed using the Perceived Stress Scale.¹⁴ Physical activity will be assessed using the Physical Activity Scale for the Elderly (PASE).¹⁵

Participant inclusion/exclusion criteria: 1) age 50+; 2) English speaking /understands English; 3) No self-reported serious mental illness or diagnosis of Alzheimer's or other dementia related disease, and a score of 27 or higher on the TICS cognitive assessment during the screening call.

Procedures

Participants will be recruited through UI Extension utilizing community partners, the Extension website, Extension newsletters, and multiple media outlets, including news releases, fliers, and social media. Upon registering for the program, participants will be contacted and invited to take part in the research study. Those interested will be screened

for inclusion into the study with a brief telephone interview which includes the TICS assessment. Participants who are eligible will be sent a consent form and baseline assessment. University of Illinois at Chicago will provide institutional review board approval. All survey assessments will be administered online unless a participant is unable to complete the survey online in which case s/he will be offered the opportunity to take the survey via phone with a researcher or to receive a paper copy with a selfaddressed, stamped return envelope. Once the

baseline assessment is completed, participants will be randomized into two groups by a member of the research team. The treatment group will receive the 12-week workshop and the waitlist control group will receive the treatment after the six-month posttest is complete (see Figure 1). The first posttest and TICS will be administered by a member of the research team to both the workshop and control groups immediately following the end of the 12-week program (3 months). The 6-month follow-up assessment and TICS will be administered 3 months after the end of the program to both the workshop and control groups by a member of the research team. Reminders to complete the survey will be sent by a research team member by email and/or phone. Participants will be provided a \$20 gift card upon completion of each survey that will be administered by a research assistant. A "reunion" event will take place three months after the last *Wits Workout* session for the workshop group only. The reunion will give participants an opportunity to reconnect informally and it will enable the research team to conduct the follow-up focus groups. Qualitative methods are particularly well suited for the assessment of simulated changes in behavior and will provide us richer detail than the surveys alone¹⁶.

Power Analysis and Sample Size Estimation. In the cognition literature, a 1-3 point decrease in the Mini Mental State Exam score has been shown to be indicative of a meaningful decline. Our primary outcome, cognitive functioning, will be assessed using the TICS -- a telephone version of Mini Mental State Exam which is administered in person. Both measures correlate highly.^{9,10} Among older adults with normal cognition, which is our target sample for this trial, an effect size of 0.29 was considered clinically meaningful.¹¹ With this more conservative effect size of .20, an alpha of .05/6 = 0.008 9adjusted for multiple outcome measures and comparisons across rural and urban samples), for 3 time points (0-12-24 weeks), power set to .80, and an estimated correlation of .50 among measures, we need a total of 208 participants. Accounting for ~15% attrition, we will target to recruit a total of 240 participants for this trial. **Data Analysis**

Quantitative data. We will conduct 3x2 repeated measures ANOVAs to examine time (pre vs. post vs. follow-up),

group (intervention vs. waitlist control), and interaction effects. The quantitative measures that will be evaluated using this statistical model include measures of social satisfaction and support, perceived well-being and quality of life, physical activity and exercise, self-efficacy, and the cognitive functioning scores. Covariates such as demographics [age, biological sex, geographic location (rural vs. urban)], and attendance to the Wits Workout program will be accounted for in the analyses. As a secondary analysis, we will also examine correlations between the demographic characteristics and the study outcomes. Drs. [name] and [name] have experience in analyzing similar large datasets from randomized controlled trials using these analysis strategies.

Qualitative data. [name] will conduct the focus groups using a guide to facilitate the discussion. The guide will include nine questions that will provide more in-depth detail about outcomes experienced by the participants (i.e. *In what ways did participating in Wits Workout impact your health behaviors?*) as well as questions that will provide details about their perception of the program (i.e. *What suggestions do you have to improve the program?*). We will audiotape and transcribe the focus groups. Three research team members will review all transcripts to develop an initial code book. We will then apply the codebook to a subsample of the transcripts individually then meet to discuss any areas where we are not coding consistently and adjust the codebook accordingly. We will then apply the same technique to another subsample of transcripts. Once we are certain that coding is consistent and the codebook is finalized, [name] will code the transcripts using NVivo QSR qualitative software. She will use an inductive thematic analysis process to analyze the data. Themes will be discussed and finalized with the research team.

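### The plan is inconsistent on whether self-rated PROMIS cognition is a primary measure, and has no rule to stop a PROMIS-only difference, open to expectation bias, being reported as improved cognitive functioning

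*Combined protocol and SAP*

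**What the plan says.** The combined protocol and SAP gives the primary measure in three places, and they do not agree.

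- **Outcome Measures:** "We will examine the effects of participation in Wits Workout on the primary outcome of cognitive functioning". The same paragraph continues "Cognitive functioning will be assessed using the PROMIS Cognitive Function- Short Form 8a" and names the TICS beside it, with no ranking of the two.
- **Hypotheses (under Overall Aims):** the first hypothesis concerns the PROMIS "self-reported cognitive function measures"; TICS scores are the second.
- **Power Analysis and Sample Size Estimation:** "Our primary outcome, cognitive functioning, will be assessed using the TICS". PROMIS does not appear in that section.

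The instruments differ in kind. Of one, the plan says "TICS is a brief, standardized test of cognitive functioning designed to be measured over the telephone". The other is a self-report; surveys are completed online, with phone or paper as alternatives.

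The trial is "a two-arm randomized controlled trial with a treatment (workshop) group and wait-list control group". Under Procedures, "Upon registering for the program, participants will be contacted and invited to take part in the research study". Randomization follows the baseline survey, and controls are offered the workshop only once the 6-month assessment is done. The documents do not mention masking of participants or assessors, an attention control, or a measure of expectancy.

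The Data Analysis section applies one 3x2 repeated measures ANOVA to all the scores. It does not say whether PROMIS, TICS or both must show benefit for a conclusion about cognitive functioning.

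**The concern.** A participant who rates their own cognition while knowing their arm is both the subject and the unmasked assessor. Those in the workshop arm sought the programme and got it; those on the waitlist sought it and were asked to wait. Hope in one group or disappointment in the other could move self-ratings with no change in cognition. A performance test is less open to this.

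At stake is the meaning of Aim 2. If PROMIS differs between arms and TICS does not, the Aims and Outcome Measures sections allow that result to be described as an effect on the primary outcome, while the power section points to TICS. A multiplicity adjustment lowers the false-positive rate when there is no bias, but it does not remove a bias. Masking the TICS caller would not protect PROMIS, because the participant does the rating.

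**Working it through.** **1. The plan's own sample size.** Inputs from the power section: effect size 0.20, alpha .05/6 (written as .008), power .80, three time points, correlation .50. Read as a between-group test in a repeated measures ANOVA with Cohen's f = 0.20, the noncentrality is

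lambda = f² × N × m / (1 + (m − 1) × rho) = 0.04 × 208 × 3 / (1 + 2 × 0.5) = 12.48.

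At alpha .008 this gives power 0.802, so 208 is reproduced. Then 208 × 1.15 = 239.2, in line with the target of 240. The sample size is not in dispute here; it supplies 208 / 2 = 104 per arm.

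**2. Inputs for the bias check.**
- 104 per arm and correlation .50: power section.
- Alpha .008: power section. The Data Analysis section states no alpha, so .05 is shown as well.
- True effect on cognition: zero (assumption).
- Shift in self-rating between arms, b: 0.2, 0.3 or 0.4 SD (assumption; the documents give no figure).

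**3. Standard error** of the difference between arms in change from baseline to one posttest, in SD units:

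SE = sqrt(2 × 2 × (1 − 0.5) / 104) = sqrt(2 / 104) = 0.139.

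**4. Chance of a significant PROMIS difference** is approximately Phi(b/SE − z), with z = 1.96 at .05 and z = 2.65 at .008.

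| Assumed shift b | b/SE | alpha .008 | alpha .05 |
|---|---|---|---|
| 0 (two-sided) | 0 | 0.8% | 5% |
| 0.2 SD | 1.44 | 11% | 30% |
| 0.3 SD | 2.16 | 31% | 58% |
| 0.4 SD | 2.88 | 59% | 82% |

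**5. Does the planned model change the picture?** The table uses one visit. For the 3x2 group-by-time interaction, with the same shift at both posttests, the noncentrality is (104 / 2) × (2b² / 3) / (1 − 0.5) = 69.3 × b², on 2 and 412 degrees of freedom. The chances at 0.2, 0.3 and 0.4 SD are 11%, 33% and 64% at .008, and 30%, 60% and 85% at .05. The one-visit figures are a fair summary.

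**6. Does sample size help?** No. With all 240 retained (120 per arm), the one-visit figures at .008 rise to 13.5%, 37% and 67%, because a larger trial detects a bias more readily.

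**The case against.** The strongest reply is that the plan already keeps the two instruments apart. They have separate numbered hypotheses, PROMIS is labelled as self-report, and the trial is sized on TICS. Read literally, a split result means that the first hypothesis is supported and the second is not. No passage says that one positive instrument is enough. This stands in part: a reader might infer that the plan permits success on PROMIS alone, but it only fails to exclude it. The inconsistency over the primary measure remains.

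A reader might also infer that an arm difference on PROMIS is to be expected, or that a PROMIS-only result is the probable outcome, because participants are told for 12 weeks that the programme works. The documents do not support this. The Intervention section lists topics such as exercise, mental challenge, social activity, sleep and stress; the Background gives the developers' purpose, not what participants are told about efficacy. There are no expectancy data. Even knowledge of arm is an inference from the workshop-versus-waitlist design, though no other reading is plausible.

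Third, perceived cognition is a legitimate target: the Background opens with subjective cognitive decline, Aim 2 claims only preliminary efficacy, and every self-reported outcome in an unmasked waitlist trial shares this weakness. That is a fair reason not to insist on moving PROMIS to the secondary outcomes. It does not justify reporting a self-rating as cognitive functioning without qualification.

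Finally, TICS has limits too, which are set out as costs of the change.

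**Conclusion.** The concern holds as a defect of definition and interpretation. The Aims, Hypotheses and Outcome Measures give PROMIS equal standing with TICS on the primary outcome, the power section names TICS alone, and no rule covers disagreement between them. In an unmasked waitlist comparison of people who signed up for the programme, a PROMIS-only difference could be due to expectation or disappointment, and nothing stops it being reported as improved cognitive functioning.

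The size is conditional. The 11% to 59% at .008 (30% to 82% at .05) follows from assumed shifts of 0.2 to 0.4 SD with no true effect, 104 per arm and correlation .50. It shows how readily this trial would declare a bias of that size significant. It does not show how probable such a bias is, and should not be read as an estimated false-positive rate for the trial.

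**What to change.** 1. Reconcile the Aims, Hypotheses and Outcome Measures with the power section, so that the claim of preliminary efficacy on cognitive functioning rests on TICS, the measure on which the trial is sized.
2. Report PROMIS Short Form 8a under its own label, as perceived (self-reported) cognitive function. Formally listing it as a secondary outcome is optional.
3. Add one sentence to Data Analysis: a PROMIS difference without a TICS difference will be reported as a change in perceived cognition in an unmasked waitlist comparison, not as improved cognitive functioning.

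The cost is wording only; data collection, visits, sample size and the analysis of PROMIS are unchanged. There are two downsides. A PROMIS-only result can no longer be presented as a primary success. The claim then rests on TICS, which is also the entry screen (27 or higher) in a sample chosen for normal cognition, so room to improve may be limited; the documents give no scale range from which to judge how far. TICS is also administered at follow-up by the research team with no stated masking of the assessor. Both limits should be acknowledged when the change is made.

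### Eligibility does not exclude people who have already attended Wits Workout, and the plan mentions no record of earlier attendance; if repeat attendees gain less, the workshop-versus-waitlist difference is attenuated, by an unknown amount

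*Combined protocol and SAP*

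**What the plan says.** The criteria, under Participant inclusion/exclusion criteria, begin "1) age 50+; 2) English speaking /understands English; 3) No self-reported serious mental illness". They continue with no diagnosis of dementia and end "and a score of 27 or higher on the TICS cognitive assessment during the screening call". That is the whole list.

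The Background and Rationale section shows that the series has been run before: "Preliminary evaluations demonstrate that this educational series serves a need in reducing isolation, increasing physical activity". It also says that UI Extension educators developed it.

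The Procedures section gives the route into the study. "Participants will be recruited through UI Extension utilizing community partners, the Extension website, Extension newsletters, and multiple media outlets" is the recruitment method, and "Upon registering for the program, participants will be contacted and invited to take part in the research study" is the point of contact. Those interested are then screened "for inclusion into the study with a brief telephone interview which includes the TICS assessment".

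Aim 2, under Overall Aims, is to examine preliminary efficacy at the end of the 12 weeks and to "explore maintenance effects at 6 months (3-months post-intervention) compared to a waitlist control".

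The Quantitative data paragraph names age, sex, rural or urban location and program attendance as covariates. The Intervention paragraph shows that this attendance is what educators record over the trial's own 12 weeks, so it does not cover earlier courses.

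**The concern.** Aim 2 is a contrast between receiving the workshop and not yet having received it. A past attendee on the waitlist is not untreated in that sense, and a past attendee in the workshop arm is repeating a course. For such people the contrast is a repeat course against past exposure only, which is a different question.

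The plan makes this foreseeable. Past attendees exist, the organisation that developed the series also recruits for the trial, and the invitation goes to people who have just asked to take the program. The plan also allows that effects may outlast the course, since it looks for maintenance three months afterwards.

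At stake are some power and the clarity of the estimate. If earlier attendance is not asked about before randomisation, the analysis can neither show how many such people were enrolled nor set them aside.

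**Working it through.** **Is the omission complete?** Four places could deal with earlier exposure:
- Eligibility: no such item.
- Screening call: the TICS is the only content named.
- Randomisation: no stratification by earlier exposure is described.
- Covariates: attendance at the trial's own workshop only.

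None mentions it.

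**Inputs from Power Analysis and Sample Size Estimation.** Effect size .20 (metric not stated), alpha .05/6 printed as 0.008, 3 time points, correlation .50, power .80, total 208.

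**Reproducing 208.** Read .20 as Cohen's f and test the group main effect in a two-arm repeated-measures ANOVA with m = 3 visits:

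λ = N × f² × m / (1 + (m − 1)ρ), with 1 and N − 2 degrees of freedom.

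At N = 208, λ = 208 × 0.04 × 3 / (1 + 2 × 0.5) = 12.48. With alpha .008 the power is 80.2%, and 208 is the smallest even N that reaches 80%. With alpha at the unrounded .05/6 it is 206. The group-by-time interaction with the same inputs needs only 64, and two independent means with d = 0.20 need 1,212 to 1,222. So 208 belongs to the group main effect.

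**Dilution model (an assumption).** A share p of each arm has attended before, and those people show a fraction r of the between-arm effect seen in newcomers:

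f_eff = 0.20 × (1 − p(1 − r)).

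The documents give neither p nor r. For p = 10% and r = 0, f_eff = 0.18 and λ = 208 × 0.0324 × 3 / 2 = 10.11.

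| Share p in each arm | Power at N = 208, r = 0 | Evaluable N for 80%, r = 0 | Power at N = 208, r = 0.5 | Evaluable N for 80%, r = 0.5 |
|---|---|---|---|---|
| 0% | 80.2% | 208 | 80.2% | 208 |
| 5% | 75.0% | 230 | 77.7% | 218 |
| 10% | 69.2% | 256 | 75.0% | 230 |
| 20% | 56.0% | 322 | 69.2% | 256 |

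If r = 1 (repeat attendees gain as much as newcomers), f_eff = 0.20 whatever p is, and nothing is lost.

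**Same model, interaction test.** λ = N × f² × m / (1 − ρ), with 2 and 2(N − 2) degrees of freedom. At N = 208, alpha .008 and r = 0, power is above 99.9% at p = 0, 99.96% at p = 10% and 99.6% at p = 20%. An f of .20 for the interaction is not the same raw difference as an f of .20 for the main effect, so this does not show that the trial is overpowered. It does show that the size of the loss depends on which test carries the conclusion, and the plan lists both.

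**The case against.** The case against is substantial on size.

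- **The premise is partly inferred.** The documents do not say how many people attended before, when, where, or how they were recruited. That they came through the same Extension channels is a fair inference from UI Extension's role, but it is not stated, and the trial also uses news releases, fliers and social media. The share could be zero. This stands.
- **A reader might infer that any past attendee, in either arm, pulls the difference toward zero, or that the comparison is biased by imbalance.** The documents support neither. Randomisation follows the baseline assessment and balances earlier exposure in expectation. Lasting benefit of similar size in both arms cancels. Attenuation also needs repeat attendees to gain less than newcomers, through lasting benefit or a ceiling on the scales, and the plan has no evidence on this. This stands.
- **The larger power losses are a worst case.** They assume no gain at all from repeating, and they apply to the group main effect. This stands, which is why the r = 0.5 figures and the interaction result are shown.
- **Evidence of carry-over is thin.** Looking for maintenance at three months does not show that a course taken at some unspecified earlier date still affects TICS or PROMIS scores. This stands.
- **The full screening script is not reproduced.** Earlier attendance may be asked about there. What can be said is that the plan does not mention recording it.
- **Admitting repeat attendees may be a reasonable choice** in a study of feasibility and preliminary efficacy. That is so, but the choice should be stated and the exposure recorded.

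None of this removes the omission: a foreseeable exposure is neither excluded nor said to be measured, and asking after randomisation would be too late to change who is enrolled.

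**Conclusion.** The point holds in a limited form. As written, past attendees are eligible and can be randomised to either arm, and the plan mentions no record of their earlier attendance. If some enrol and gain less from repeating than newcomers gain from a first course, the estimated workshop effect is attenuated and the analysis could not show it.

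The size cannot be derived from the documents. Under the assumed shares of 5% to 20% per arm, power for the group main effect falls from 80% to between 75% and 56% if past attendees gain nothing, and to between 78% and 69% if they keep half the effect. It does not fall if there are no past attendees or if they gain as much as newcomers, and the loss is negligible for the interaction test with the same inputs. This is a cheap improvement of minor to moderate importance, not a flaw that invalidates the comparison.

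**What to change.** Add to the Participant inclusion/exclusion criteria: has not previously attended any Wits Workout session. Ask this as one question in the existing telephone screening call. Past attendees who register can still be offered the program outside the study.

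If the sponsor prefers to keep them, record earlier attendance before randomisation, report the count by arm, and pre-specify in the Data Analysis section a sensitivity analysis that leaves them out.

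The cost is one eligibility line and one screening question, by protocol and IRB amendment. With exclusion, a few registrants become ineligible and must be replaced. With recording only, nobody is lost, but the main estimate still mixes first-time and repeat attendees.

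### Individual randomisation with no household rule can split people who register together between workshop and waitlist, biasing the arm difference modestly toward zero

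*Combined protocol and SAP*

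**What the plan says.** Four features of the combined protocol and SAP bear on this point.

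- **Entry route (Procedures).** People first sign up for the class and are then approached for the trial: "Upon registering for the program, participants will be contacted and invited to take part in the research study".
- **Unit of allocation (Procedures).** Once the "baseline assessment is completed, participants will be randomized into two groups by a member of the research team". No household or pair unit is described, and no stratification or blocking.
- **Local pools (Sample and Table 1).** The plan is for "120 treatment and 120 delayed treatment controls) in three urban and five rural areas of Illinois". Table 1 pairs 20 workshop with 20 waitlist places at each urban site, and 12 with 12 at each rural site. Allocation within site is implied by these quotas but not stated.
- **Eligibility.** The list begins "Participant inclusion/exclusion criteria: 1) age 50+; 2) English speaking /understands English" and goes on to mental illness, dementia and the TICS threshold. Nothing limits enrolment to one person per household.

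The comparison needs controls to stay untreated for the whole study: "the waitlist control group will receive the treatment after the six-month posttest is complete". The power section has no allowance for a diluted contrast. The planned ANOVA has no household term, and no measure of control exposure is described.

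**The concern.** A weekly social class for people aged 50 and over, advertised through community partners and local media, may attract couples or housemates who sign up together. If they are randomised separately, one may attend while the other waits at home. The topics include "participating in social activities; e) getting enough sleep; and f) reducing stress" as well as exercise and mental challenges. Several of these match the trial's own outcomes: sleep, stress, physical activity and social satisfaction. A control living with an attendee could pick up some of that content or join in the changed behaviour.

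Such spill-over has a known direction: it moves the control mean toward the workshop mean and biases the estimated difference toward zero. A larger sample would restore power but would not remove the bias. The plan as described collects nothing from which the number of split households could be reported afterwards.

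**Working it through.** **1. Reproduce the stated sample size.** Inputs from Power Analysis and Sample Size Estimation: effect size 0.20, alpha 0.008, three time points, power 0.80, correlation 0.50, total 208. The metric of the effect size is not stated. Read as Cohen's f for the group main effect in a repeated-measures ANOVA:

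- noncentrality λ = N·f²·m / [1 + (m − 1)ρ] = 208 × 0.04 × 3 / (1 + 2 × 0.5) = 12.48, on 1 and 206 df;
- power at alpha 0.008 = 0.802, and 208 is the smallest even N that reaches 0.80.

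The stated figure is reproduced, with nothing in it for dilution.

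**2. Chance that a co-registered pair is split.** If the Table 1 quotas are filled within site: 20/39 = 51% (urban) or 12/23 = 52% (rural). Simple 1:1 allocation gives 50%, so the result barely depends on whether allocation is within site.

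**3. Size of the dilution.** Two quantities are needed, and the documents give neither:

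- q, the share of participants in same-household pairs: assumed 10–30%;
- c, the share of the effect passed to a cohabiting control: assumed 25–50%.

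About q/2 of controls would live with an attendee: 6 of 120 at q = 0.10, 12 at 0.20, 18 at 0.30. The difference shrinks by the fraction qc/2, so f becomes 0.20 × (1 − qc/2).

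| q | c | Shrinkage qc/2 | f | Power at N = 208 | Equivalent N factor, 1/(1 − qc/2)² |
|---|---|---|---|---|---|
| 0.10 | 0.25 | 1.25% | 0.1975 | 0.790 | 1.025 |
| 0.10 | 0.50 | 2.5% | 0.195 | 0.777 | 1.052 |
| 0.20 | 0.25 | 2.5% | 0.195 | 0.777 | 1.052 |
| 0.20 | 0.50 | 5% | 0.190 | 0.750 | 1.108 |
| 0.30 | 0.50 | 7.5% | 0.185 | 0.722 | 1.169 |

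Using 51–52% in place of one half raises the largest shrinkage to 7.8% (power 0.719).

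**4. Cost of allocating households together.** With within-pair outcome correlation rho (also assumed, 0.20–0.30), the variance factor is about 1 + q·rho. It runs from 1 + 0.10 × 0.20 = 1.02 to 1 + 0.30 × 0.30 = 1.09.

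**5. Net effect on precision.** The N factor recovered is about 1 + qc, against a cost of 1 + q·rho, so joint allocation improves power only when c exceeds rho. At q = 0.20 and c = 0.50 it recovers 1.108 for a cost of 1.04 to 1.06. At q = 0.20 and c = 0.25 it recovers 1.052 for the same cost, which is roughly break-even.

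**The case against.** The case against is substantial, and much of it stands.

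- **Size.** No part of the documents mentions couples or households. Both q and c are assumptions, as is rho. With few pairs or little spill-over the loss is about one power point.
- **Mechanism.** The plan describes one in-person hour a week and no homework or take-home material. That content is carried into the home is an inference. How much of an effect on a cognitive test such as the TICS could reach someone who never attended is unknown.
- **Null results.** A reader might infer that a null result could not be told apart from dilution. The figures do not support that: the largest shrinkage tabulated takes 0.20 to 0.185.
- **Uncontrolled access.** A reader might also infer that controls are free to join a workshop early. The documents say otherwise: "The waitlist control participants (n=120) will be offered the workshop after the 6-month study period is completed", and leaders record attendance. The gap concerns indirect exposure through a housemate.
- **Unmeasured exposure.** The survey forms are not reproduced, only the scales named. The documents are silent on an exposure question; they do not rule one out.
- **Dependence on the power reading.** The loss to 0.72 belongs to the group main effect. Under the time-by-group interaction with f = 0.20 and the same conventions, power at 208 stays above 0.999 even at 7.5% dilution. That convention is generous (it needs only 64 participants and does not reproduce 208), but the power figures are specific to one reading.

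The structural point remains: participants are randomised, both arms come from the same local registrants, and nothing keeps co-registered household members together. The direction of any resulting bias is not in dispute.

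**Conclusion.** The point holds as a modest, avoidable bias toward zero. If household members register together, about half of those pairs would be split, and any spill-over shrinks the arm difference. On assumed ranges of 10–30% of participants in pairs and 25–50% of the effect passed on, the shrinkage is about 1–8%. Power at 208 falls from 0.80 to between 0.79 and 0.72, on the group-main-effect reading with f = 0.20 and alpha 0.008. The documents supply neither range, so the true figure could lie outside them, and it is zero if no pairs register. This does not undermine the trial. It is a cheap improvement to make before randomisation, justified mainly by removing a bias that sample size cannot remove.

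**What to change.** 1. At the existing screening call, ask whether another member of the household has registered, and record the answer as a baseline flag.
2. Allocate members of one household together, as a single unit in the allocation list.
3. Account for household in the analysis, with a household cluster term in a mixed model or cluster-robust standard errors, so that jointly allocated pairs are not analysed as independent.
4. Optionally, add one item to the 3- and 6-month surveys in both arms on exposure to the program or its materials, and report control exposure descriptively.
5. If a sensitivity analysis is wanted, or if some households have already been split, define it by the baseline household flag and exclude co-registered household members from **both** arms. Dropping only exposed controls would select on one arm and break the randomised comparison.

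**Cost.** One screening question, a rule in the allocation list, a small change to the model and, if adopted, one survey item per follow-up. The statistical price is a variance factor of about 1.02–1.09 (q of 0.10–0.30, rho of 0.20–0.30) and slight imbalance in site totals. When spill-over is low, precision roughly breaks even or falls slightly, and the return is then the removal of bias.
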